$$A_{ik} = \beta_0 + \beta_1 t_{ik} + \beta_2 x_i + \beta_3 (x_i \times t_{ik}) + v_{0i} + v_{1i} t_{ik} + \epsilon_{ik}$$

Where A_{ik} is the aggression score for the i^{th} participant at time point k ; β_0 is the aggression score at baseline; x_i is the dummy-coded treatment group variable ($x_i=0$ for PCT and $x_i=1$ for CBT-A); β_1 is the linear effect of time for the PCT group; β_2 is the condition difference at baseline; β_3 is the condition difference in terms of the linear effect over time; v_{0i} and v_{1i} are subject-specific random effects representing the deviation of each subject from the group intercept and linear trend; and ϵ_{ik} is random residual effects (Hedeker & Gibbons, 1997).

Mixed models are able to handle missing data. Pattern mixture models can be used to describe the effects of missing data on outcome and to provide estimates by averaging over missing data (Hedeker & Gibbons, 1997); and Intent to Attend the next session data can be used to determine if participant drop-out or loss to follow-up meets the assumption of ignorable attrition (Leon, Demirtas, & Hedeker, 2007).

Power Analysis and Sample Size Determination

The paucity of studies examining outcomes of treatment for anger and aggression in Veterans with PTSD, and the inconsistency in measures used across studies, makes it difficult to estimate effect size for sample size estimations. One study reported pre- to post-treatment decreases in aggression with an effect size in the medium range (Marshall, et al., 2010). This is consistent with more general studies of anger management therapies, where effect sizes have been reported in the medium to large range depending upon the measure used and the population sampled (Del Vecchio & O'Leary, 2004; DiGiuseppe & Tafrate, 2003).

Effect sizes for sample size determination of the larger RCT will be calculated based on differences between pre-treatment and post-treatment scores on the measures of aggressive behavior. Comparisons will be made using a two-sample t-test. Because there is a risk of inaccurate estimation of effect sizes in pilot studies (Kraemer, 1992), we will employ recommended procedures for improved characterization of effect sizes derived from pilot studies. These include close consultation with clinicians who have used the treatment (i.e. [name]), and accounting for the effect size uncertainty by constructing confidence intervals around the observed effect sizes.

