Eligibility for research participation is not contingent on eligibility or enrollment for VA care. This is important for this study because there is a subset of Veterans with PTSD who are unlikely to voluntarily seek treatment in the VA (see Spont et al., 2014). Any Veteran who is not enrolled for care within VA will be offered a Notice of Privacy Practices, and we will document the receipt thereof. This study does not involve procedures that are likely to cause any risk to pregnant women or unborn children. Therefore, pregnant women will not be excluded from participation in the study.

In order to maximize the data for understanding whether CBT-A may assist in reducing aggression, the treatment will be administered independent of concurrent other PTSD psychotherapies. To evaluate the relationship between treatment for PTSD and treatment for anger and aggression we will collect information about participation in therapy for PTSD prior to study participation or during the follow-up assessment phase; however, endorsement of therapy for PTSD prior to or after the study treatment phase will not be exclusionary. If a participant expresses interest in therapy for PTSD during the treatment component of the study, the participant will be offered a referral for treatment within the VA (i.e. CPT or PE). Participants who receive such referrals will be informed that if they plan to initiate treatment for PTSD immediately they will no longer be eligible for participation in the study but will be compensated for their partial participation, and that if they are interested in being screened again after completing therapy for PTSD they will be eligible to do so. Participants

will continue to be eligible for participation in the current study if they plan to initiate treatment during the 6-month post-treatment assessment phase.

It is important to acknowledge that the proposed intervention does not address PTSD symptoms other than anger and aggression, and that participation in this research study should not be seen as a substitute or alternative to receiving empirically-supported treatment (EST) for PTSD. In fact, among the rationales for providing the proposed treatment to individuals with PTSD is that reductions in anger and aggression might increase the likelihood of seeking, benefiting from, and completing EST for PTSD.

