The VA is committed to disseminating empirically-supported treatments for PTSD including PE and CPT. The VISN-6 MIRECC has a close relationship with the Durham VA OEF/OIF/OND Clinic, and research clinicians routinely do “warm hand-offs” of Veterans interested in treatment for PTSD by taking them directly to the Clinic and introducing them to the staff. With Veterans’ consent, MIRECC clinicians also enter consults for Veterans directly into CPRS, thereby facilitating clinical assessment and treatment for PTSD and other psychiatric or medical problems.

Consistent with routine procedure within the VISN-6 MIRECC, throughout the screening, treatment, and assessment process of the proposed study Veteran participants will be educated about PTSD and about CPT and PE; will be provided with resources for accessing these treatments; and will be encouraged to participate in one of these empirically-supported therapies. Participants will be informed that while they cannot participate in this study while receiving psychotherapy for PTSD, they are free to discontinue participation in the study at any time if they wish to initiate specific treatment for PTSD. They will also be provided with information about the OEF/OIF/OND Clinic or other appropriate resources and about PE and CPT at screening, and they will be encouraged to follow up with EST for PTSD either immediately or upon completion of participation in this study. Finally, PE and CPT will be discussed throughout the group sessions. PE and CPT will specifically be a focus of discussion in the 1st session during the review of the history of PTSD; during the 8th session when we review the principles behind trauma-focused therapy; and during the last session when follow-up treatment options and referrals are discussed.

Subject Recruitment

The recruitment site for this study will be the Durham VAMC. This region is heavily populated by active duty, National Guard, and Reservist military personnel. There are currently over 9,000 Afghanistan/Iraq-era Veterans enrolled at the Durham VAMC.

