Subjects who were recruited through the VISN 6 MIRECC's Post-Deployment Mental Health Data Repository Re-Contact Database will be asked to allow their current contact information (e.g., phone number and address) to be updated in the Re-Contact Database. In addition, subjects recruited through the VISN 6 MIRECC'S Post-Deployment Mental Health Repository will also be asked if the data collected as part of their participation in the current study may be added to the Post-Deployment Database in the MIRECC's data repository (IRB # 01706). This written permission will be sought through the ICF. The purpose of feeding data back into the data repository is to increase the data available with which to answer future, unique research questions pertaining to post-deployment mental health and is part of the purpose of the creation of the VISN 6 MIRECC Post-Deployment Mental Health data repository.

Study Interventions

Intervention Description: Cognitive-Behavioral Therapy for Anger and Aggression in Combat Veterans

Cognitive-Behavioral Therapy for Anger and Aggression in Veterans with PTSD (CBT-A) is a 12-week manualized group treatment protocol that is grounded in up-to-date research, and that has been designed to specifically address the cognitive, affective, physiological arousal, and behavioral components of combat PTSD-related anger and aggression. Sessions last 120 minutes. All participants will be asked to come to sessions about 15 minutes early so that they can complete weekly assessment measures. The first session orients participants to the structure and philosophy of the program, provides a historical overview of PTSD, and introduces the model of how a PTSD-related affective style contributes to problems managing anger and aggression. The remaining 11 sessions follow a standard format: 1) practice relaxation training (15-20 minutes); 2) review homework, introduce new material, and engage in group activities focused on implementing new skills and behaviors (70-80 minutes); and 3) review problems or concerns of group members. Appendix C presents a table summarizing each session, how sessions have been tailored for combat Veterans with PTSD, and references supporting these unique components of the intervention.

Description of Active Comparison Condition: Present Centered Therapy

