Present Centered Therapy (PCT) was developed to provide an active, manualized treatment comparison condition for psychotherapy trials. PCT is designed to control for nonspecific factors of therapy such as contact with a trained therapist, rationale for treatment, and instillation of expectancy for therapeutic gains. The therapeutic approach was drawn from Yalom's group therapy model, which utilizes interpersonal process, supportive techniques, identification of response options, encouragement of adaptive reactions, and focus on the "here-and-now." Previous large-scale randomized clinical trials of Veterans with PTSD have found reduced PTSD symptoms in the PCT comparison condition (Schnurr et al., 2003), and a survey of practice patterns within the VA suggests that similar present-focused approaches are routinely employed by VA mental health providers (Rosen et al., 2004). Consistent with recommendations in the PCT manual, training will emphasize the approach rather than specific interventions.

Treatment Fidelity Ratings for Interventions

In order to examine treatment fidelity and counselor competence, we will videotape all counseling sessions using a VA-approved videorecording device, the Toshiba Camileo x200. This camera is not moved off site, as the groups are held at the Durham VA Medical Center's main campus. The recordings will then be reviewed by another trained study staff member using the Yale Adherence and Competence Scale system [YACS; (Carroll, 2000)]. Because of the nature of group therapy, we believe it would be less confusing for the reviewer to be able to see the participants (e.g., to determine who is talking). For this reason, we will videotape the sessions rather than audiotape, and it is likely that participants' voices and faces will be captured on the recordings. Study participants are informed during the informed consent process that they will not be allowed to participate in the treatment if they are not willing to be recorded. Because this study uses an informed consent form and HIPAA authorization, and videotaping is described fully therein, we will not require that form 10-3203 be signed. Recordings will be moved from the camera to the VA shared drive, S:\Nicotine Research\Study Information\Study Logbooks\gCBT for An.Agg\Therapy Recordings. Recordings will be retained as per VA Records Control requirements.

Justification for Inclusion of Non-Veteran Collateral Reporters

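### Starting PTSD therapy in the treatment phase ends study participation, and no visible text continues outcome assessment, so the pre-post t-test that sizes the larger RCT loses those allocated participants

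*Combined protocol and SAP*

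**What the plan says.** **The exit rule.** Selection of Subjects deals with a participant who becomes interested in PTSD therapy during the treatment component. The participant is offered a referral and told this: "if they plan to initiate treatment for PTSD immediately they will no longer be eligible for participation in the study but will be compensated". Payment covers the part completed. Re-screening after that therapy is allowed. The same section adds that "while they cannot participate in this study while receiving psychotherapy for PTSD, they are free to discontinue participation in the study" whenever they wish. Therapy begun in the six-month follow-up phase does not end eligibility. The stated reason for the rule is that "the treatment will be administered independent of concurrent other PTSD psychotherapies". Anyone already receiving or planning PTSD psychotherapy for the treatment phase is excluded at entry. Screening Procedures separately allows discretionary withdrawal from the study when a participant cannot take part in sessions.

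**Assessments.** Table 1 places the Conflict Tactics Scale (CTS) and the aggressive driving questions, the two primary measures, at pre-treatment, post-treatment, 3 months and 6 months. Neither is marked under treatment sessions; only the WHODAS, DAR and PCL are. Collateral reporters also complete the CTS, with packets mailed at the three later time points.

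**Analysis.** Power Analysis and Sample Size Determination derives the effect size for the larger RCT from pre- to post-treatment differences in aggressive behavior, compared by a two-sample t-test. Subject Recruitment assumes 15% drop-out, leaving 30 completers, and commits to using every one of the 36 randomized participants in every analysis. Aim 1 lists group drop-out and retention to 6 months as separate objectives.

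**The concern.** The rule joins two events that an intention-to-treat analysis keeps apart: stopping the allocated treatment and ceasing to be followed. A participant who changes therapy after allocation is, on the visible text, no longer a study participant, and no provision keeps their outcome assessments going.

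The plan also promotes the triggering event. Participants are urged throughout to take up evidence-based PTSD therapy, and one sentence says "they will be encouraged to follow up with EST for PTSD either immediately or upon completion of participation in this study".

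Two things are at stake. The first is the effect estimate meant to size the larger trial, because the t-test can use only people with both a pre- and a post-treatment score. The second is the retention objective. For these participants the protocol itself converts treatment drop-out into loss to follow-up, so retention no longer measures willingness to be followed.

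**Working it through.** **1. The plan's own figure.** 36 × (1 − 0.15) = 30.6, against 30 stated, so it reproduces. The implied losses are 36 − 30 = 6, from all causes. The documents do not say how many would leave to start PTSD therapy.

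**2. What a leaver contributes.** Four self-reported primary scores are scheduled, none of them at treatment sessions. Someone who exits mid-treatment has 1 of 4. A change score needs two, so none exists. Whether collateral CTS packets continue after the Veteran exits is not stated.

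**3. Mixed model.** In the displayed equation baseline is one of the repeated outcomes, so the participant is retained. A single time point says little about change, however. I assumed variances of 0.6 (intercept), 0.3 (slope, with time scaled 0 to 1) and 0.4 (residual), and an intercept-slope correlation of 0 or −0.3. With three leavers per arm, their baseline scores then keep 11% to 21% of the slope information that their full data would add.

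**4. Precision of the t-test.** The plan intends confidence intervals but gives no level; 95% is assumed. In SDs of change:
- 15 per arm: 1.96 × √(2/15) = 0.716 (by t with 28 df, 2.048 × √(2/15) = 0.748).
- 18 per arm: 1.96 × √(2/18) = 0.653.

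The interval is about 10% wider (0.716/0.653 = 1.10) if all 6 losses came from this rule, and less otherwise.

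**5. Selection bias in the t-test.** Bias = (fraction removed in one arm − fraction removed in the other) × gap in mean change between leavers and stayers. The gap is assumed to be 0.5-1.0 SD and equal in both arms.

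| Leavers by arm | Difference in fractions | Bias (SD) |
|---|---|---|
| 3 v 3 | 0 | 0 |
| 1 v 0 | 1/18 = 0.056 | 0.028-0.056 |
| 5 v 1 | 4/18 = 0.222 | 0.111-0.222 |

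The 5 v 1 row is an outer bound. It needs every expected loss to come from these rules and to fall almost entirely in one arm, which nothing in the documents shows.

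Under the variances in step 3, the mixed model gives the same values when leavers and stayers have equal baselines. With leavers' baselines 0.5 SD higher or lower it gives 0.014-0.069 at 1 v 0 and 0 at 3 v 3.

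**6. Consequence for the larger RCT.** The plan states no alpha, power or numeric effect. Assume two-sided 0.05, 80% power and a completer effect of 0.5 SD: n per arm = 2 × (1.960 + 0.842)² / 0.5² = 62.8, so 63. Suppose one of 18 CBT-A participants left with change 0.5-1.0 SD worse than the stayers. The all-randomized effect is then 0.5 − 0.028 = 0.472 to 0.5 − 0.056 = 0.444, which needs 71 to 80 per arm. If the leaver did better, the error would run the other way.

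**7. Price of following leavers.** If PTSD therapy added an assumed 0.5 SD to their later change, the as-allocated difference would depart from the difference without concurrent therapy by 0.056 × 0.5 = 0.028 SD at 1 v 0.

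**The case against.** Much can be said for the plan. No sentence says outright that assessments stop; that is inferred from loss of eligibility, from payment for partial participation and from the absence of any provision to continue. Known planners are excluded at entry, so only those who change their minds are affected. Any drop-out, whatever the cause, lacks a change score, so the t-test gap is partly a general missing-data gap. The commitment to use all 36 is justified by the mixed model, where these people remain. Data Analysis names pattern-mixture models and Intent-to-Attend data for testing whether attrition is ignorable. Keeping CBT-A apart from concurrent therapy is deliberate. Some leavers will withdraw consent whatever the protocol says.

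All of this limits the size of the point without removing it. The missing-data tools are optional and attached to the mixed model, and the t-test has no rule for a missing post-treatment score. This loss, unlike ordinary drop-out, is created by the protocol and can be avoided.

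Two stronger readings are tempting.

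- **That CBT-A loses more people than PCT.** The plan says "PE and CPT will specifically be a focus of discussion in the 1st session during the review of the history of PTSD", and for CBT-A that "The first session orients participants to the structure and philosophy of the program, provides a historical overview of PTSD"; the PCT description mentions no such session. But the passage on PE and CPT names no arm and has them discussed throughout the groups. The PCT remark that "training will emphasize the approach rather than specific interventions" concerns therapist training, and Appendix C was not available. An arm difference is possible, not established.
- **That good responders leave.** The statement that "reductions in anger and aggression might increase the likelihood of seeking, benefiting from, and completing EST for PTSD" is a general rationale for treating anger, not evidence about departures mid-treatment. The sentence urging immediate uptake may also refer to advice given at screening, although encouragement during treatment is stated separately.

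**Conclusion.** The point holds in a limited form. On the visible text, an allocated participant who starts PTSD therapy in the treatment phase leaves the study with only a baseline self-reported primary score. That participant cannot enter the t-test that sizes the larger RCT, so the commitment to use all 36 is not met for that analysis. Drop-out and retention also become one event for these participants.

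A reader might infer that they vanish from every analysis, or that the pilot estimate is seriously biased. Neither follows. The mixed model as displayed keeps them, and collateral reports may continue. The bias is 0 with balanced removal and 0.03-0.06 SD at 1 v 0, well inside a half-width of about 0.72 SD. The number of leavers, the direction and the gap are all unknown; the 0.5-1.0 SD gap is an assumption. The conclusion would change if the consent pages or Figure 2 provide for assessment after exit, in which case the sections would still need to be made consistent. Priority: minor to moderate for a 36-person pilot.

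**What to change.** Leave the rule on who stops group sessions as it is, and reconcile Selection of Subjects, Subject Recruitment and Screening Procedures:

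- Separate stopping group sessions from leaving the study.
- Keep seeking the scheduled post-treatment, 3-month and 6-month assessments, participant and collateral, from everyone allocated unless consent is withdrawn. Offer participants a mailed option at post-treatment.
- Record the start date of any PTSD therapy begun in the treatment phase, and report departures by arm.
- Count a re-screened participant once, under the first allocation.
- State that the main result is the as-allocated effect, including any later PTSD therapy.
- Add a sensitivity analysis that excludes scores taken after PTSD therapy begins. Use the pattern-mixture and Intent-to-Attend methods already named, with the weekly DAR and PCL as predictors of departure.

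**Cost.** Protocol and consent wording, and a few extra mailings. Collateral returns are paid at $10 each: 3 × $10 = $30 per leaver, or 6 × $30 = $180 if all six expected losses were leavers. Participant payments stay within the $400 planned for complete participation. The main downside is that some post-treatment scores will reflect another active therapy, which is why the sensitivity analysis is needed.
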